1.1 PROTOCOL SYNOPSIS

Title	Phase II study of combination chemotherapy and immune checkpoint blockade with Pembrolizumab in the perioperative and maintenance treatment of locoregional gastric or GE junction adenocarcinoma.
Short Title	Perioperative chemotherapy and pembrolizumab in locally advanced gastric cancer (Merck Internal Reference: MISP 52339)
Protocol Number	AAAQ9871
Phase	Phase II
Methodology	Single arm, multi-center, Phase II study with interim safety analysis
Study Duration	30 months (for efficacy results)
Study Centers	Columbia University Medical Center, New York; Weill Cornell Medical Center, New York; Washington University in St. Louis, St. Louis; Rhode Island Hospital/Lifespan Cancer Institute, Providence, Rhode Island
Objectives	
Primary Objective:
 
 1. To evaluate the efficacy of combination therapy with immune checkpoint blockade and chemotherapy as determined by the pathologic complete response rate (pCR). Pathological complete response is defined as no invasive disease within an entirely submitted and evaluated gross lesion, and histologically negative nodes. 
Secondary Objectives:
 
 2. To determine the efficacy of combination therapy with immune checkpoint blockade and chemotherapy by overall response rate (ORR), and used in the perioperative period in eradicating micrometastatic disease as measured by disease free survival (DFS) and overall survival. 3. To compare paired tissue and serum samples (pre-treatment and post-treatment) from individually treated patients to explore the immune effects of combination therapy and predictors of response as determined by IHC, flow cytometry, and genomic analysis of tumor and immune cells 
Exploratory Objective:
 
 1. To determine if pathologic complete response (pCR) rate correlates with recurrence free survival (RFS)

Number of Subjects	There will be an estimated 38 patients enrolled in this protocol. We estimate that at least 28 subjects will proceed to surgery and be evaluable for the primary outcome of pCR. All subjects will be available for the secondary analysis of ORR, DFS, and OS.

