3.3 Exploratory Objectives & Hypotheses

Objective: To identify tumor and patient characteristics that predict response and correlate with long term outcomes following treatment with combination Pembrolizumab and chemotherapy.

Hypothesis: We hypothesize that baseline markers of immune activation such as Tumor Infiltrating Lymphocytes and CD8+ lymphocytes will correlate with response to pembrolizumab and that responders to pembrolizumab will have distinct tumor immune phenotype as determined by immunohistochemistry compared to non-responders.

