8.1.2 Secondary Endpoint

The secondary endpoints are ORR, DFS and OS. DFS is defined as time from Cycle 1 Day 1 treatment administration to the first documented event of: disease progression, disease recurrence following surgery (preferably biopsy proven), or death- whichever occurs first. Overall Survival (OS): time from Cycle 1 Day 1 treatment administration to death due to any cause.

The secondary hypothesis of this study is that combination therapy with immune checkpoint blockade and chemotherapy used in the perioperative period will eradicate micrometastatic disease and improve disease free survival (DFS).

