8.1.3 Exploratory and Ancillary Studies

Gene expression profiles and IHC will be quantified as continuous variables and results will be compared between baseline and surgical specimens (pre therapy and post 12 weeks of combination therapy). We expect that some samples will be inadequate for analysis but anticipate 35 paired specimens. With 35 paired samples of pre and post specimens, we will have 80% power to detect a change of 0.50 standard deviation with a two-sided alpha of 0.05.

We will analyze changes in immune profiles between subjects (prior to and after treatment) using paired t-tests or non-parametric test if the data is not normally distributed. Moreover, we will compare immune profiles (using presence of TILs and PD-L1 expression among other measurements) between those who have a good response (defined as pathCR, or 24 month DFS) to those who do not have a good response. Given that we expect a small number of patients with pathCR, we will compare the data descriptively using summary statistics such as mean, median and ranges.

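### Section 8.1.3 relates continuous immune markers to DFS only through a descriptive 24-month yes/no grouping; a per-marker Cox estimate with its interval would be a cheap improvement to this exploratory analysis

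*Combined protocol and SAP*

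**What the plan says.** Section 8.1.3 sets the marker scale: "Gene expression profiles and IHC will be quantified as continuous variables". Its only analysis linking markers to outcome contrasts "those who have a good response (defined as pathCR, or 24 month DFS) to those who do not have a good response". The method and its reason come together: "Given that we expect a small number of patients with pathCR, we will compare the data descriptively using summary statistics", namely mean, median and ranges. No test, model or interval is named for this contrast.

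The one power statement in that section concerns something else, the change from baseline to surgical specimen: "With 35 paired samples of pre and post specimens, we will have 80% power to detect a change of 0.50 standard deviation". The significance level for that comparison is 0.05, two-sided.

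Section 8.1.2 makes DFS a time: "DFS is defined as time from Cycle 1 Day 1 treatment administration to the first documented event". Section 8.2.1 analyses it by Kaplan-Meier for the whole cohort, including a 24-month estimate with its 95% interval, but with no marker term.

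Two objectives depend on marker-outcome work. The exploratory objective in Section 3.3 is to "identify tumor and patient characteristics that predict response and correlate with long term outcomes". Secondary objective 3 in the synopsis (Section 1.1) is to explore, among other things, "predictors of response as determined by IHC, flow cytometry, and genomic analysis of tumor and immune cells".

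**The concern.** Section 3.3 asks which characteristics go with long-term outcome, and DFS is the long-term outcome that Section 8.1.3 uses. As planned, the answer would be two columns of summary statistics, with no measure of how strongly a marker is associated with DFS and no statement of uncertainty.

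The grouping has three further weaknesses:

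- It treats an event at month 3 like one at month 23 and ignores every event after month 24.
- It gives no rule for a patient censored event-free before month 24. Leaving such patients out keeps the early relapses and drops people who were doing well.
- It does not say whether pathCR and 24-month DFS form one composite or two separate groupings.

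At stake is the usefulness of an exploratory analysis. The pCR test, the sample size and patient care are not affected.

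**Working it through.** **1. The plan's own figure.** Paired t-test, 35 pairs, 0.50 SD, two-sided 0.05: noncentral t with 34 degrees of freedom and noncentrality 0.5 × √35 = 2.96 gives power 0.82. The stated 80% is reproduced. It covers pre/post change and says nothing about prediction of outcome.

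**2. Does the stated reason cover both halves of good response?** For pathCR, at the design rates of 3% and 15% (Section 8.1.1): 0.03 × 28 = 0.84 and 0.15 × 28 = 4.2 patients. With all 38, the counts are 1.1 and 5.7. A descriptive comparison is reasonable there. For DFS, the documents give no 24-month rate. If it were 50-60%, then 0.50 × 38 = 19 to 0.60 × 38 ≈ 23 patients would be event-free at 24 months and about 15-19 would not. On that assumption neither group is small.

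**3. Is another marker-by-DFS analysis planned?** Sections 8.1.2, 8.1.3 and 8.2.1 set side by side give a time-to-event definition, a descriptive split, and a whole-cohort Kaplan-Meier curve. None contains a marker-by-DFS model, test or interval.

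**4. Illustration of what the split gives up.**

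*From the documents:* 38 enrolled (synopsis), 35 paired specimens (Section 8.1.3), 18 months' accrual and 36 months' trial duration (Section 1.0), 30 months for efficacy results (synopsis).

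*Assumed:* a normal marker in SD units, hazard ratio 1.75 per SD, exponential DFS, 24-month DFS of 50% or 60% at the marker mean, uniform accrual, no other dropout, two-sided 0.05.

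The hazard is (−ln S24 / 24) × 1.75^x: 0.0289 per month at x = 0 for 50%, and 0.0213 for 60%. The Cox score test is z = U/√V. U sums, over events, the patient's marker minus the risk-set mean; V sums the risk-set variances. The comparator is a two-sample t-test of event-free at 24 months against event before 24 months, leaving out patients who cannot be classified. The plan does not contain this t-test; it is supplied so that the split has a power at all.

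Simulated power, Cox versus split, n = 38, 3,000 runs per scenario:

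| Follow-up | 24-month DFS 50% | Gain | 24-month DFS 60% | Gain |
|---|---|---|---|---|
| Analysis at month 42 (all followed at least 24 months) | 73% v 61% | 12 | 64% v 54% | 10 |
| Analysis at month 36 | 67% v 52% | 15 | 58% v 45% | 13 |
| Analysis at month 30 | 61% v 32% | 29 | 51% v 30% | 21 |
| Every patient stopped at exactly 24 months | 65% v 61% | 4 | – | – |

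Simulation error is about 1 point per power figure, so a gain can move by a point or two. Repeat runs and runs at n = 35 agree to that accuracy, and the exact-24-month gain is about 2-5 points across both DFS rates. At 50% DFS, the split can classify about 31 of 38 patients at month 36 and about 23 at month 30. With no marker effect, both tests reject in 4.4-5.6% of runs.

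**5. Where the gain comes from.** The last row isolates the cost of cutting time at 24 months: 2-5 points. The rest comes from events after month 24 and from using patients not yet followed that long.

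**6. How long disease status is scheduled to be known.** Section 7.2.2.7.2 lists completion of treatment among the points at which imaging stops, and Section 7.2.5.3.2 then moves completers to telephone survival contact. Counting from Cycle 1 Day 1, with the last chemotherapy dose at week 6: 6 + (4 to 6) + (6 to 10) + 17 × 3 = 67 to 73 weeks. Counting from the end of cycle 3 (week 9) gives 70 to 76 weeks. At 4.345 weeks per month the span is about 15.4 to 17.5 months. If DFS is known only to about 17 months, Cox power is about 44-55% for n = 35-38, and the split cannot confirm any patient as event-free at 24 months.

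**The case against.** The strongest reply is that this is exploratory work, reported descriptively in a section titled as exploratory, with no decision or sample size resting on it. That stands, and it sets the weight of the point. It does not supply a reason for treating DFS like pathCR, and exploratory work still benefits from an estimate with an interval.

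A reader might go further than the documents allow in four ways:

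- **That the plan loses power.** It specifies no test here, so there is no planned power to lose. The split's power figures belong to a t-test added for comparison.
- **That the trial hypothesises a link between baseline TIL or CD8+ and DFS.** Section 3.3 states that hypothesis for response to pembrolizumab, which a responder comparison fits. Long-term outcome appears in the objective, not in the TIL/CD8+ hypothesis.
- **That cutting at 24 months is itself costly, or that the groups will be equal.** The cut alone costs about 2-5 points, and the documents give no 24-month DFS rate.
- **That the data for the larger gains are sure to exist.** Sections 2.1 and 5.8 promise disease follow-up for subjects who stop treatment without recurrence, but no imaging schedule backs this after treatment completion.

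Two cautions apply to any replacement. Section 4.2.3 contemplates about 500 genes, and even 20 independent tests at 0.05 carry a 1 − 0.95^20 = 64% chance of at least one false positive. Section 2.1 exempts pathological complete or near-complete responders from submitting resection tissue, so surgical-specimen markers may be missing for the best responders.

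Section 2.1 also names OS in PD-L1 positive tumors as a secondary objective. That is a marker-linked survival objective, but it concerns OS in a subgroup, not a continuous marker against DFS.

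**Conclusion.** The point holds as a cheap improvement to an exploratory analysis. The descriptive treatment is justified for pathCR and not for DFS. No section plans an estimate, interval or model for marker against DFS, and the 24-month grouping cannot place patients censored early. These conclusions rest on the text alone.

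The size is illustrative and depends on the assumed DFS rate, hazard ratio and marker distribution. At a hazard ratio of 1.75 per SD, n = 35-38 and 24-month DFS of 50-60%, the Cox advantage is about 9-12 points at month 42, 13-17 at month 36 and 21-29 at month 30, but only 2-5 if all follow-up ends at 24 months. Cox power itself is moderate, and only about 44-55% if disease status is known to about 17 months. The gap in scheduled imaging is a separate matter that a change of model does not repair; Cox regression merely uses whatever follow-up there is.

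**What to change.** In Section 8.1.3, state that pathCR and DFS are handled separately. Keep pathCR versus non-pathCR descriptive, and replace the 24-month DFS half with wording such as:

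*Each pre-named continuous baseline marker (TIL, CD8+, PD-L1) will be related to DFS by univariable Cox regression in treated subjects with an evaluable baseline sample. The hazard ratio per SD will be reported with its 95% CI. Subjects without an event will be censored at their last disease assessment. Results are hypothesis-generating; any larger gene panel will be analysed with false-discovery-rate control. Surgical-specimen markers, if modelled, will use DFS counted from surgery among resected subjects, and the report will state that pathological complete or near-complete responders may lack tissue.*

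The cost is one paragraph and a little analysis, with no new patients, visits or assays. The downsides are an assumed proportional, log-linear effect and few events: about 16-23 at months 36-42 under the assumptions above, fewer if disease assessment ends earlier. That allows one marker per model.

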8.2 Statistical Analysis Plan Details

8.2.1 Efficacy Endpoints

Pathologic complete response (pCR): The number and proportion of subjects with pCR will be reported along with the exact binomial confidence interval. We reject the null that the pCR rate is 3% or less if 3 or more out of the 28 patients achieve pCR.

Disease Free Survival (DFS) and Overall Survival (OS): The Kaplan-Meier method will be used to evaluate all time to event endpoints. Median DFS and OS will be estimated and reported with 95% confidence intervals. Moreover, we will report the estimated DFS at 24 months with 95% confidence intervals.

Overall Response Rate (ORR): The number and proportion of subjects with initial RECIST 1.1 measurable disease who have complete response (CR) or partial response (PR) at any time will be reported along with the exact binomial confidence interval.

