2.0 TRIAL DESIGN

2.1 Trial Design

This is a non-randomized, multi-site, open-label trial of pembrolizumab and chemotherapy in subjects with gastric or gastroesophageal junction adenocarcinoma. Up to 38 subjects may be enrolled in a single cohort, for a sample of 28 evaluable subjects, to assess the efficacy of combination therapy with standard peri-operative chemotherapy in resectable gastric or GE junction adenocarcinoma. The trial was initiated at 2 sites and two additional sites were subsequently added to increase enrollment.

All study subjects will receive standard of care chemotherapy for 3 cycles prior to and 3 cycles following surgery in combination with Pembrolizumab with an additional cycle of Pembrolizumab (4 total) in the pre-operative period. Additionally, subjects will complete 12 months of maintenance Pembrolizumab (14 additional doses to complete 17 post-operative cycles) following completion of post-operative chemotherapy. The primary efficacy endpoint will be **pathologic complete response (pCR) rate** among all enrolled subjects. Recurrence or disease progression will be determined based on RECIST 1.1 and investigator assessment.

Adverse events will be monitored throughout the trial and graded in severity according to the guidelines outlined in the NCI Common Terminology Criteria for Adverse Events (CTCAE) version 4.0.(As referenced in Appendix 13.2)

After the end of treatment, each subject will be followed for 30 days for adverse event monitoring. Serious adverse events and Events of Clinical Interest (ECI) will be collected for 90 days after the end of treatment or 30 days after the end of treatment if the subject initiates new anticancer therapy, whichever is earlier. Subjects who discontinue treatment for reasons other than disease recurrence will have post-treatment follow-up for disease status until disease recurrence, withdrawing consent, or becoming lost to follow-up. All subjects will be contacted by telephone for overall survival until death, withdrawal of consent or the end of the study, whichever comes first.

[figure not shown]

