5.8 Subject Withdrawal/Discontinuation Criteria

Subjects may withdraw consent at any time for any reason or be dropped from the trial at the discretion of the investigator should any untoward effect occur. In addition, a subject may be withdrawn by the investigator or the Sponsor-Investigator if enrollment into the trial is inappropriate, the trial plan is violated, or for administrative and/or other safety reasons. Specific details regarding discontinuation or withdrawal are provided in Section 7.1.4 – Other Procedures.

Even if a subject discontinues trial treatments, they will be encouraged to continue to participate in collection of data regarding the endpoints, including DFS and OS.

A subject must be discontinued from the trial treatments for any of the following reasons:

- The subject or legal representative (such as a parent or legal guardian) withdraws consent.
- Confirmed radiographic disease progression or recurrence
- Unacceptable adverse experiences as described in Section 5.2.1.2
- Intercurrent illness that prevents further administration of treatment
- Investigator's decision to withdraw the subject
- The subject has a confirmed positive serum pregnancy test
- Noncompliance with trial treatment or procedure requirements
- The subject is lost to follow-up
- Completed 12 months of uninterrupted treatment with pembrolizumab following surgical resection or 17 administrations of study medication, whichever is later.

Note: 12 months of study medication is calculated from the date of first dose following surgical resection.

- Administrative reasons

The End of Treatment and Follow-up visit procedures are listed in Section 6.0 (TRIAL FLOW CHART) and Section 7.1.5 (Visit Requirements). After the end of treatment, each subject will be followed for 30 days for adverse event monitoring (serious adverse events will be collected for 90 days after the end of treatment as described in Section 7.2.3.1). Subjects who discontinue for reasons other than progressive disease will have post-treatment follow-up for disease status until disease progression or recurrence, withdrawing consent or becoming lost to follow-up. After documented disease progression each subject will be followed by telephone for overall survival until death, withdrawal of consent, or the end of the study, whichever occurs first.

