7.2.2.7.2 Tumor Imaging During Trial

The first on-study imaging assessment will be performed 11 weeks after Cycle 1 Day 1 (78 days +/- 14 days) and will be used to assess response to chemotherapy and eligibility for surgery. Imaging may be conducted prior to Cycle 4 dosing (of Pembrolizumab) if clinically indicated as assessed by local routine practice. Subsequent imaging will be performed

following surgical resection and will begin within 7 days of Cycle 5 day 1 (first post-operative cycle) which is expected to not be later than 8 weeks from the time of surgery (65 days +/- 14 days). Beginning from the first post-operative scan, subsequent tumor imaging will be performed every 12 weeks (+/- 7 days).

Imaging should continue to be performed until whichever one of the following occurs first:

- disease progression limiting a subject from surgical resection
- recurrence of disease following surgical resection
- completion of study treatment
- withdrawal of consent
- death
- end of study

Imaging should follow calendar days and not be delayed for any dose interruptions that may occur (except for delays post-operatively).

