7.2.5.3.2 Survival Follow-up

Once a subject experiences confirmed disease progression or completes 17 cycles of post-operative therapy, the subject moves into the survival follow-up phase and should be contacted by telephone every 12 weeks to assess for survival status until death, withdrawal of consent, or the end of the study, whichever occurs first.

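### The protocol gives conflicting follow-up rules for patients who complete treatment, so recurrences in roughly the last 7 to 9 months before the 24-month DFS estimate may have no scheduled ascertainment, and Section 8 has no DFS censoring rule

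*Combined protocol and SAP*

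**What the plan says.** Section 8.1.2 measures DFS from Cycle 1 Day 1 to progression, recurrence after surgery or death. Section 8.2.1 names Kaplan-Meier and adds: "Moreover, we will report the estimated DFS at 24 months with 95% confidence intervals". Section 8.1.3 also uses 24-month DFS, as an alternative to pCR, to define the good-response group for the immune-profile comparison. The synopsis calls DFS a key secondary efficacy outcome.

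Follow-up of patients who complete treatment is described in several places:

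- Section 7.2.2.7.2 schedules imaging every 12 weeks after surgery and stops it at the first of several events, one of which is "completion of study treatment". Flow chart footnote i gives the same interval without a stop.
- Section 7.2.5.3.2: "Once a subject experiences confirmed disease progression or completes 17 cycles of post-operative therapy, the subject moves into the survival follow-up phase". That phase is a telephone call every 12 weeks about survival status.
- Section 5.8 includes this among its reasons for discontinuing treatment: "Completed 12 months of uninterrupted treatment with pembrolizumab following surgical resection or 17 administrations of study medication, whichever is later". It then says: "Subjects who discontinue for reasons other than progressive disease will have post-treatment follow-up for disease status until disease progression or recurrence". It places the telephone phase later: "After documented disease progression each subject will be followed by telephone for overall survival".
- Section 2.1 has a rule like that in 5.8: "Subjects who discontinue treatment for reasons other than disease recurrence will have post-treatment follow-up for disease status until disease recurrence".

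Section 8.2.5.3.1 says how a suspected recurrence is confirmed and dated. The flow chart and Section 7.2.1.5.3 also collect new anticancer therapy after treatment, every 12 weeks in the flow chart.

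**The concern.** A completer without recurrence falls under both 5.8 and 7.2.5.3.2. One rule continues disease-status follow-up; the other replaces it with survival calls. Neither 2.1 nor 5.8 gives an interval or visit for the disease checks it requires. If the word discontinue in those sections is taken to mean early stopping only, the conflict becomes a plain gap, with the same effect on the estimate.

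Month 24 lies well beyond the last dose, so the 24-month figure depends on which rule a site follows. It also depends on how the analyst treats event-free completers. Sections 8.1.2, 8.2.1 and 8.2.5 do not say whether they are censored at the last disease assessment or the last contact, and they give no data cut-off. That choice could be made after the data are seen, and it can move the estimate up or down.

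**Working it through.** **Timeline.** Surgery is 4 to 6 weeks after the last chemotherapy dose (Section 5.2.2; week 6 if counted from the Cycle 3 infusion) or after completion of Cycle 3 (Section 7.2.5.2.1; week 9). Cycle 5 starts 6 to 10 weeks after resection (Section 5.2.2). One month is 4.348 weeks.

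- Cycle 5 Day 1: 6 + 4 + 6 = week 16, to 9 + 6 + 10 = week 25.
- 17 post-operative cycles (Sections 2.1 and 7.2.5.2.3): add 16 x 3 = 48 weeks. The last dose is at weeks 64 to 73, or 14.7 to 16.8 months. The 16-month average treatment length in Section 1.0 lies in this range. Month 24 is 7.2 to 9.3 months later.
- Synopsis wording (3 combination cycles plus 17 additional): add 19 x 3 = 57 weeks. The last dose is at weeks 73 to 82, or 16.8 to 18.9 months. Month 24 is 5.1 to 7.2 months later.

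**Size of the bias.** Every input here is assumed: exponential DFS with S(24) = 0.50 or 0.60; mean m = 10 months from recurrence to death; 5% of events are deaths without recurrence; a share e = 0.25 of patients event-free at the last dose T stopped early but are still fully followed; no later recurrence in a completer is captured. Write h = -ln S(24)/24.

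The share of patients who would recur between T and month 24 and still be alive at month 24 is

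M = 0.95 x h/(1/m - h) x [S(24) - S(T) exp(-(24 - T)/m)].

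*Rule A, completers stay at risk through survival calls.* These recurrences are missed in completers, so the bias is +(1 - e)M.

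*Rule B, completers censored at the last scan (taken as T) unless they die by month 24.* Let q = [S(T) - S(24) - M]/S(T), the chance of death by month 24 given event-free at T. Everyone left in the risk set after T then leaves only through an event, so the Kaplan-Meier value at 24 months is e S(24)/[e + (1 - e)q].

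| S(24) | T (months) | S(T) | M | Rule A bias | q | Rule B estimate | Rule B bias |
|---|---|---|---|---|---|---|---|
| 0.50 | 14.7 | 0.654 | 0.093 | +7.0 | 0.093 | 0.391 | -10.9 |
| 0.50 | 16.8 | 0.616 | 0.077 | +5.8 | 0.062 | 0.421 | -7.9 |
| 0.60 | 14.7 | 0.731 | 0.080 | +6.0 | 0.070 | 0.496 | -10.4 |
| 0.60 | 16.8 | 0.700 | 0.067 | +5.0 | 0.047 | 0.526 | -7.4 |

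Biases are in percentage points. If half of the later recurrences are captured, Rule A halves to +2.5 to +3.5. Under the synopsis cycle count Rule A gives +3.8 to +5.8. The Rule B figures count deaths to month 24. Counting later deaths as well keeps those patients in the risk set at month 24, which shrinks the downward shift and can reverse it, so the result also depends on the cut-off.

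**Would censoring at the last documented assessment be enough?** Suppose all recurrences are captured, but only a share p of event-free completers has an assessment reaching month 24 and the rest are censored at T. With G = S(24)/S(T), the estimate is S(24) x [e + (1 - e)p]/[e + (1 - e)(1 - (1 - p)G)].

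- S(24) = 0.50, T = 14.7, G = 0.765: p = 0.5 gives 0.438 (-6.2 points); p = 0.8 gives 0.480 (-2.0).
- S(24) = 0.60, T = 16.8, G = 0.858: p = 0.5 gives 0.553 (-4.7); p = 0.8 gives 0.585 (-1.5).

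Disease-free status therefore has to be collected as completely as recurrence.

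**Data cut-off.** Section 1.0 gives 18 months of enrollment and the synopsis 30 months for efficacy results. With uniform accrual (assumed), (30 - 24)/18 = 1/3 of patients, about 13 of 38, could have 24 months of follow-up at that cut. At 36 months it is 2/3, about 25 of 38.

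**The case against.** The strongest reply is that Section 5.8 already settles the matter. It says patients will have disease-status follow-up, and completion is among its discontinuation reasons. If sites follow 5.8 with comparable assessments for all patients, the bias is about zero. That stands as a description of 5.8, but 7.2.5.3.2 gives the same patients a different instruction, and 5.8 has no schedule.

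Several stronger readings are tempting, and the documents do not support them:

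- *That the 24-month estimate rests wholly on unscheduled ascertainment.* Events up to about month 15 to 17 come from scheduled scans, deaths are sought every 12 weeks, and the anticancer-therapy query may flag some recurrences.
- *That the end of imaging itself contradicts 5.8.* Section 7.2.2.7.2 ends protocol scans; 5.8 asks for disease status without requiring scans. The two can coexist. The direct conflict is between 5.8 and 7.2.5.3.2.
- *That DFS follow-up is merely voluntary.* Section 5.8 does say that "they will be encouraged to continue to participate in collection of data regarding the endpoints, including DFS and OS", but the same section also states the firm rule quoted above.
- *That the bias is necessarily upward.* Rule B goes the other way.
- *That about half or more of the 38 would be at risk at month 24 if only ascertainment were complete.* At the 30-month cut, accrual alone limits this to about 38 x (0.50 to 0.60)/3 = 6 to 8 patients.

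It is also fair that the estimate has no test or threshold. With 38 patients and no other censoring its 95% half-width would be 1.96 x sqrt(S(1 - S)/38), about 16 points at S = 0.50 to 0.60. The shifts above are smaller than that, but they are systematic and the interval does not reflect them.

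**Conclusion.** The point holds. The conflict between 5.8 and 7.2.5.3.2, the missing interval and the missing censoring rule can be read directly from the text. The gap of 7 to 9 months (5 to 7 under the synopsis count) follows from the stated schedule if 7.2.2.7.2 and 7.2.5.3.2 are followed.

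The size is illustrative: about +5 to +7 points under Rule A and -7 to -11 under Rule B, on wholly assumed inputs and with no later recurrence captured. Partial capture would make the Rule A figure smaller.

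The consequence is limited to a descriptive secondary estimate and the good-response grouping in 8.1.3. The primary pCR analysis is not affected. It should be corrected before the DFS analysis. Confidence is medium, because the effect depends on what sites actually do after treatment.

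**What to change.** - Reconcile 7.2.5.3.2 and 7.2.2.7.2 with 2.1 and 5.8, so that a single rule has disease status followed in completers to at least 24 months from Cycle 1 Day 1.
- At the existing 12-weekly contacts, record for every completer either recurrence (date and method, confirmed as in 8.2.5.3.1) or disease-free status with the date of the latest routine-care assessment. Add no protocol scans.
- In 8.2.1, censor event-free patients at the last contact at which disease status was documented. Collect that status in the same way for patients with and without recurrence, and do not accept a survival-status call alone. State the data cut-off.
- Add a sensitivity analysis that censors all completers at the last protocol scan and does not count their later events. It avoids the imbalance in Rule B, but near month 24 it relies on the early stoppers: under the assumptions above, at most about 38 x 0.25 x (0.50 to 0.60) = 5 to 6 patients, fewer at an early cut-off.
- Separately, reconcile the synopsis cycle count with 2.1 and 7.2.5.2.3. Which count is intended is for the sponsor to state.

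The cost is wording in these sections and a few more fields at calls already scheduled. Routine-care ascertainment will be less uniform than protocol scans, and the report should say so.
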